4.2 Number of Patients

Sample size calculation is performed using one proportion equality test using the exact test to achieving an 80% power at the 5% level of significance. With the expectation of an -15% of improvement of acute radiation proctitis (30% to 15%), the total estimated patients number in a single-arm trial required is 64. Consider the patient with incomplete data and drop-out rate of 10%, the total estimated number of sample size is 72. Sample size calculation was performed using PASS software (Power Analysis and Sample Size version 2021, NCSS, Kaysville, Utah, USA).

4.3 Schedule of Activities

Time-Event scheme(評估時程表):

Phase	Screening	Short-course radiation therapy	Treatment										Surgery watch-and wait
			Chemotherapy										
Week	0	1	3 ± 1	5 ± 1	7 ± 1	9 ± 1	11 ± 1	13 ± 1	15 ± 1	17 ± 1	19 ± 1	22-24	
Clinic or ward visit	X	X	X	X	X	X	X	X	X	X	X	X	
Screening/Efficacy													
ICF/ Informed consent form	X												
Inclusion/Exclusion criteria	X												
Medical and surgical history	X											X	
Physical exam (with digital exam)	X		X				X				X		
Colonoscopy (Vienna Rectoscopy Score)	X		X				X				X		
Colonoscopy biopsy (tumor and normal tissue)	X		X				X				X		
Pelvis MRI (or transrectal ultrasound)	X											X	
Computed tomography	X											X	
Biopsy and tissue proof	X												
Tumor analysis	X		X				X				X		X
Adverse event evaluation			X	X	X	X	X	X	X	X	X	X	
Peripheral blood analysis	X		X		X			X				X	
Complete blood count/ WBC differentiation	X		X	X	X	X	X	X	X	X	X	X	
Serum carcinoembryonic antigen/ CA 19-9	X			X			X				X		

Immune profiling

➤ Peripheral blood

The presence of tumors is often linked to a significant reduction in both effector and memory T cell populations, a shift from type 1 to type 2 immune responses, and diminished effector T cell proliferation. Preclinical studies have shown that curcumin can counteract these immunosuppressive effects by preserving T cell populations, expanding central memory (TCM) and effector memory (TEM) T cell subsets, reversing the type 2 immune bias, and restoring T cell proliferation in tumor-bearing hosts. Curcumin also suppresses regulatory T cell (Treg) function by downregulating the secretion of immunosuppressive cytokines such as TGF- β and IL-10. Importantly, it enhances the cytotoxic activity of effector T cells against cancer cells. These findings highlight curcumin's potential as an immunomodulatory agent capable of mitigating tumor-induced suppression of cell-mediated immunity and augmenting antitumor immune responses [23]. To determine whether these findings are applicable to patients, we plan to use BD FACSsymphony high-parameter flow cytometry to assess T effector cell function before and after combinatorial treatment. This will be done using a validated antibody panel available at Chang Gung Memorial Hospital (Table 1).

人類毒性T及輔助T細胞染色分析服務-27色

No	Specificity	Fluorochrome
1	CD14	FVS510 (BV510)
2	CD19	
3	Live	
4	CD3	BUV805
5	PD-1	PE-Cy7
6	CD8	BUV496
7	panGDT (TCR γ δ)	BV605
8	CCR7	BV750
9	CD4	BUV563
10	CD45RA	BV480
11	CD161	PE-Cy5
12	LAG-3	BV650
13	GB	PE-CF594
14	Foxp3	R718
15	CXCR5	BV711

No	Specificity	Fluorochrome
1	CTLA-4	BV421
2	Perforin	PerCP-Cy5.5
3	IFN- γ	BUV395
4	p16	BV570
5	IL-17	PE
6	CCR4	BB790
7	CCR6	BB630
8	IL-4	BUV737
9	KLRG-1	APC
10	CXCR3	BUV661
11	IL-9	BV786
12	Pu.1	BUV615
13	CD25	BB515
14	CD45RO	APC-H7

Table 1. Tentative antibody panel for BD FACSsymphony high-parameter immunophenotyping. (The antibody panel is subject to modification based on the experimental conditions.)

To evaluate whether curcumin can suppress pro-inflammatory cytokines during radiotherapy and chemotherapy, we plan to employ a cytokine array to comprehensively assess cytokine levels before and after total neoadjuvant treatment. Additionally, we aim to monitor circulating tumor DNA (ctDNA) dynamics—a promising non-invasive

biomarker—by measuring ctDNA levels pre- and post-treatment. This approach will allow us to explore potential correlations between ctDNA fluctuations and treatment response or clinical outcomes, supporting the use of liquid biopsy for real-time monitoring and assessment of therapeutic efficacy. As a control group, we will include blood samples from patients with chronic liver disease but without HCC, collected from the Human Tissue Biobank at Chang Gung Memorial Hospital.

*We will use the Milliplex cytokine array (Human Cytokine/Chemokine Magnetic Bead Panel IV; Catalog #HCYP4MAG-64K), which includes targets such as BAFF, Blys, BRAK, CXCL14, CCL28, CXCL16, HCC-4, CCL16, HMGB1, IFN β , IL-14, IL-19, IL-24, IL-28B, IL-32 α , IL-34, IL-35, IL-36 β , IL-1F8, IL-37, IL-1F7, IL-38, IL-1F10, MIP-4, MPIF-1, CCL23, and YKL40.

(Note: The panel may be adjusted depending on experimental needs.)

➤ Tumor biopsy

To investigate whether curcumin enhances the antitumor efficacy and mitigates normal tissue toxicity of radiotherapy and chemotherapy, we will employ multiplex immunohistochemistry to perform high-dimensional spatial profiling of both tumor and adjacent normal colon mucosal tissues from colorectal cancer (CRC) patients. This cutting-edge multiplex imaging technique allows for simultaneous detection of dozens of protein markers on formalin-fixed paraffin-embedded (FFPE) samples, preserving spatial context and cellular interactions within the tumor microenvironment [24].

Using multiplex immunohistochemistry, we will comprehensively characterize immune cell infiltration patterns, including CD4+ and CD8+ T cells, regulatory T cells (Tregs), macrophages (M1 and M2 phenotypes), and dendritic cells, as well as assess expression levels of immune checkpoint molecules such as PD-1, PD-L1, CTLA-4, and CD47 on both immune and tumor cells. We will also evaluate stromal components, cytokine-associated markers, and markers of tissue damage or repair to assess treatment-induced changes in both tumor and normal mucosa. By comparing immune cell composition, activation states, and checkpoint expression in tissues from curcumin-treated versus untreated cohorts, we aim to delineate how curcumin modulates the immunological landscape of CRC. This will help determine whether curcumin not only amplifies local and systemic antitumor immunity but also confers a protective effect against treatment-induced inflammation and injury in adjacent normal tissues [25].

5. Study Population

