4.1 Overall Design

This phase II single-arm study is aimed to recruit 72 mid-to-low locally advanced rectal cancer patients who need neoadjuvant chemotherapy and radiotherapy. The pre-operative evaluation, including completed colonoscopy, neck-to-abdomen computed tomography, pelvis *magnetic resonance imaging*, and serum carcinoembryonic antigen, are arranged as a current practice guideline. After the patients agree to participate, a daily dose of 3g of BCM-95® curcumin is given as the chemotherapy starts. The curcumin therapy is continued during the whole neoadjuvant chemotherapy and radiation therapy. A complete blood count is checked during each cycle of chemotherapy.

Moreover, additional biochemical examinations with liver and renal function and adverse events (CTCAE version 5) and the criteria of the Radiation Therapy Oncology Group (RTOG) and European Organisation for Research and Treatment of Cancer (EORTC) are examined every 3 cycles of chemotherapy. The curcumin treatment is ended along with the completion of chemotherapy. An additional colonoscopy will be arranged 2 to 3 weeks after the radiation therapy completed to evaluate acute proctitis by Vienna Rectoscopy Score. After completion of the chemoradiation, colonoscopy and pelvis magnetic resonance imaging are conducted to evaluate the tumor response. Based on each surgeon's clinical judgment, the patient receives either curative surgery or a watch-and-wait strategy.

Run-in Cohort (n=6) Design

Study Design

This trial will begin with a run-in cohort of 6 patients receiving high-bioavailability curcumin (BCM-95) in combination with standard neoadjuvant chemoradiotherapy (nCRT) for mid-low-rectal cancer. The purpose of the run-in phase is to confirm safety, tolerability, and feasibility prior to expanding enrollment to the full Phase II cohort.

Objectives

- Primary Objective (Run-in cohort):
To evaluate the incidence of dose-limiting toxicities (DLTs), particularly hepatotoxicity and gastrointestinal adverse events (AEs), during curcumin administration with concurrent chemoradiotherapy.
- Secondary Objectives:
 - To confirm feasibility of oral curcumin administration and patient adherence.
 - To monitor preliminary gastrointestinal protective effects (e.g., radiation proctitis, diarrhea).
 - To validate safety monitoring and study logistics prior to full expansion.

Patient Population

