5.1 Inclusion Criteria

Treatment group

Inclusion criteria:

- (A) Males and females more than 20 years of age
- (B) Signed informed consent
- (C) Patients with a pathologically proven rectal adenocarcinoma located less than 10 cm to the anus.

- (D) Clinical staging (AJCC 8th ed.): T2-4 N0 M0 or T any N1-2 M0
- (E) Distal metastasis has been excluded by imaging study: by chest-to-pelvic computed tomography or Positron Emission Tomography
- (F) Preoperative pelvic staging by pelvic Magnetic Resonance Imaging (preferred) or trans-rectal ultrasound
- (G) Patients with WHO/ECOG performance scale 0 or 1

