5.2 Exclusion Criteria

Treatment group

Exclusion criteria:

- (A) Refuse to sign the informed consent
- (B) Distal metastasis revealed by the imaging study
- (C) Patients does not receive radiotherapy
- (D) Unable to receive further curative resection
- (E) Patients receive tumor resection before the neoadjuvant treatment
- (F) Patients have history of more than 5 Gy of pelvic radiation
- (G) Patients in pregnancy or lactation status
- (H) Patients have allergic history to curcumin, 5-fluouracil or oxaliplatin
- (I) Patients of childbearing potential can not cooperate with appropriate contraceptive method (oral, injectable, or implantable hormonal contraceptive; tubal ligation; intra-uterine device; barrier contraceptive with spermicide; or vasectomized partner)
- (J) Patients with any concurrent malignancy; patients with history of malignancy should be cancer-free for more than 5 years
- (K) Patients with New York Heart Association (NYHA) class III or IV heart failure, unstable angina pectoris, unstable cardiac arrhythmia or tachycardia (heart rate > 100 beats/minute)
- (L) Patients have concurrent uncontrolled medical conditions, such as illness ongoing or requiring IV antibiotics, severe chronic renal failure (eGFR <30 mL/min/1.73m²) or severe active hepatitis(AST/ALT>3x upper normal limit) ` Total Bilirubin>2 mg/dl...etc.
- (M) Patients with previous or current drug abuse
- (N) Patients underwent major surgery within 28 days of study enrollment (except diverting colostomy)
- (O) Patients have Familial Adenomatosis Polyposis Coli (FAP), Hereditary Non-Polyposis Colorectal Cancer (HNPCC), active Crohn's disease or active ulcerative Colitis
- (P) Patients have known dipyrimidine dehydrogenase deficiency (DPD)
- (Q) Patients with congenital iron metabolic or hematopoietic diseases
- (R) Patients with synchronous colon cancer
- (S) The Patients with hematologic abnormalities (INR > 1.5, white blood cell (WBC) count < 3,000/ μ L, absolute neutrophil count (ANC) < 1,500/ μ L, platelet count <**

100,000/ μ L, hemoglobin < 9.0 g/dL not caused by tumor treatment) or known hematologic diseases (aplastic anemia, myelodysplastic syndrome (MDS), leukemia, malignant lymphoma, multiple myeloma, hereditary hematologic diseases such as thalassemia, sickle cell anemia, etc.).

(T) The patient has diabetes mellitus

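### The blood control group named for the cytokine and ctDNA work has a different disease and cannot inform the stated question about curcumin (minor, translational only)

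*Protocol*

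**What the plan says.** All of the following is in the protocol.

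- **Question.** The cytokine work in section 4.3 (Immune profiling, Peripheral blood) is introduced as "To evaluate whether curcumin can suppress pro-inflammatory cytokines during radiotherapy and chemotherapy".
- **Contrast within patients.** The same paragraph plans to "comprehensively assess cytokine levels before and after total neoadjuvant treatment", and to monitor ctDNA by "measuring ctDNA levels pre- and post-treatment", relating its changes to treatment response or clinical outcome. The time-event table schedules peripheral blood analysis at screening and at later visits.
- **Control group.** The paragraph then closes by naming the control: "we will include blood samples from patients with chronic liver disease but without HCC, collected from the Human Tissue Biobank". It gives no reason for the choice and no contrast in which the samples will be used.
- **Population and design.** Section 5.1 requires "Patients with a pathologically proven rectal adenocarcinoma located less than 10 cm to the anus". Section 4.1 states: "This phase II single-arm study is aimed to recruit 72 mid-to-low locally advanced rectal cancer patients".
- **Comparators named elsewhere.** For the tissue work, section 4.3 speaks of comparison "in tissues from curcumin-treated versus untreated cohorts". For trial outcomes, section 11.2.5 names other clinical trials and the centre's own retrospective neoadjuvant chemoradiation data.

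**The concern.** A control group for a question about curcumin should resemble the treated patients in everything except curcumin. The named controls are defined by disease of another organ. Hepatocellular carcinoma plays no other part in the protocol; the similar abbreviation in the cytokine panel list is an analyte.

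Because the trial has one arm, this is the only control group named for the blood analyses. Sections 11 and 11.2 list between-group tests for continuous variables (t-test, Mann-Whitney). An analyst following the text could compare cytokine levels in rectal cancer patients with levels in liver-disease patients, obtain a small p-value and report it as an effect of curcumin. Biobank samples and assays would also be spent on a comparison that does not answer the question.

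**Working it through.** The protocol gives no control-group size, effect size or power for this comparison, so there is no figure to reproduce. The check is what each available contrast can estimate. For one cytokine, taking effects as additive for illustration, write:

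- R: mean level in trial patients before treatment
- T: mean change over the neoadjuvant course from chemoradiotherapy, tumour response and time
- K: mean change due to curcumin, the quantity asked about
- L: mean level in the liver-disease controls, whatever their treatment history
- T': mean change in rectal cancer patients on the same regimen without curcumin

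The contrasts are:

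1. Trial patients before treatment against the controls: R − L. Curcumin does not enter.
2. Trial patients after treatment against the controls: (R + T + K) − L = (R − L) + T + K. Even with K = 0 this is non-zero whenever (R − L) + T is non-zero, and its sign says nothing about the sign of K.
3. Trial patients after against before: (R + T + K) − R = T + K. This is the paired contrast already planned.
4. The paired change against the change in rectal cancer patients without curcumin: (T + K) − T' = K + (T − T'). This equals K only if the two groups are comparable, so that T = T'.

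Contrast 2 minus contrast 1 is T + K, which is contrast 3. L cancels, so the liver-disease samples add nothing about K beyond what the paired samples already give. Used alone, contrast 2 adds the disease difference R − L to the two effects already mixed in contrast 3.

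For ctDNA, the stated aim is to correlate changes in trial patients with their own response or outcome. Only trial patients' data enter that correlation, so the control has no role in it.

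Of the four contrasts, only the fourth isolates K, and only under the comparability assumption. It is also the type of comparator that the tissue text and section 11.2.5 point towards.

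**The case against.** The strongest reply is that the text assigns these samples to no test. Tumour-free blood can serve as a background reference for an assay, the paired before-and-after contrast is already in the plan, and nothing that decides the trial rests on this sentence. Much of that stands. The use of the control is not spelled out, and an assay-background role is possible. But the protocol does not state that role. It calls the samples a control group, in the paragraph that sets out to evaluate curcumin, so the sentence needs correcting or explaining.

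Four stronger readings are tempting, and the documents do not support them:

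- **Conflict with eligibility.** A reader might set the control group against the exclusion of "severe active hepatitis(AST/ALT>3x upper normal limit" in section 5.2. That criterion is listed for the treatment group and covers severe active disease only. It does not govern biobank controls, and it does not exclude chronic liver disease as such.
- **Known characteristics of the controls.** A reader might assume that they have inflamed livers and have never had radiotherapy or chemotherapy. The protocol says neither. The argument needs only that they are defined by a different disease and that nothing gives them the trial's treatment.
- **Removal as a cure.** A reader might think that deleting the control and relying on each patient's own baseline would show what curcumin does. It would not: contrast 3 is T + K. That limit comes from the single-arm design and remains after the control is removed.
- **Text carried over from a liver cancer project.** This is a plausible explanation of the wording, but only a guess, and the point does not depend on it.

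**Conclusion.** The point holds as a minor one. As written, the control group cannot inform the question stated in the same paragraph, because a difference from trial patients combines disease, treatment and curcumin. The ctDNA aim does not need it.

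Its reach is small. Cytokines and ctDNA are not among the primary, secondary or exploratory endpoints; the one molecular exploratory endpoint, in the synopsis, concerns rectal tumour and adjacent tissue compared with databases. A reader might infer that the trial's main result or its sample size is compromised by this sentence. Neither is: the primary endpoint is a clinical toxicity outcome, and the planned 72 patients derive from a proctitis rate.

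The conclusion rests on two readings. First, the control sentence applies to both the cytokine and the ctDNA work; this is the natural reading from its position after both, though the text does not say so. Second, the word control means a comparator for the treated patients. If only an assay background was meant, the defect is one of wording.

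**What to change.** In section 4.3 (Immune profiling, Peripheral blood):

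1. Delete the sentence naming the liver-disease controls, or replace them with stored blood from rectal cancer patients given the same neoadjuvant regimen without curcumin, drawn at matching times, if such samples exist. State that this would still be a non-randomised comparison.
2. Keep the planned within-patient change from before to after treatment as the main contrast. Add that, without such a comparator, it is descriptive and not attributable to curcumin.
3. If the liver-disease samples are wanted only as a tumour-free assay background, state that purpose and exclude them from any test of curcumin effect.

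The minimum change is a few sentences of wording, and deletion saves biobank samples and assays. The replacement comparator is optional and carries the cost of finding and assaying suitable stored samples. Sample size, eligibility and the primary analysis do not change.

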5.1 Inclusion Criteria

Treatment group

Inclusion criteria:

- (A) Males and females more than 20 years of age
- (B) Signed informed consent
- (C) Patients with a pathologically proven rectal adenocarcinoma located less than 10 cm to the anus.

- (D) Clinical staging (AJCC 8th ed.): T2-4 N0 M0 or T any N1-2 M0
- (E) Distal metastasis has been excluded by imaging study: by chest-to-pelvic computed tomography or Positron Emission Tomography
- (F) Preoperative pelvic staging by pelvic Magnetic Resonance Imaging (preferred) or trans-rectal ultrasound
- (G) Patients with WHO/ECOG performance scale 0 or 1

5.2 Exclusion Criteria

Treatment group

Exclusion criteria:

- (A) Refuse to sign the informed consent
- (B) Distal metastasis revealed by the imaging study
- (C) Patients does not receive radiotherapy
- (D) Unable to receive further curative resection
- (E) Patients receive tumor resection before the neoadjuvant treatment
- (F) Patients have history of more than 5 Gy of pelvic radiation
- (G) Patients in pregnancy or lactation status
- (H) Patients have allergic history to curcumin, 5-fluouracil or oxaliplatin
- (I) Patients of childbearing potential can not cooperate with appropriate contraceptive method (oral, injectable, or implantable hormonal contraceptive; tubal ligation; intra-uterine device; barrier contraceptive with spermicide; or vasectomized partner)
- (J) Patients with any concurrent malignancy; patients with history of malignancy should be cancer-free for more than 5 years
- (K) Patients with New York Heart Association (NYHA) class III or IV heart failure, unstable angina pectoris, unstable cardiac arrhythmia or tachycardia (heart rate > 100 beats/minute)
- (L) Patients have concurrent uncontrolled medical conditions, such as illness ongoing or requiring IV antibiotics, severe chronic renal failure (eGFR <30 mL/min/1.73m²) or severe active hepatitis(AST/ALT>3x upper normal limit) ` Total Bilirubin>2 mg/dl...etc.
- (M) Patients with previous or current drug abuse
- (N) Patients underwent major surgery within 28 days of study enrollment (except diverting colostomy)
- (O) Patients have Familial Adenomatosis Polyposis Coli (FAP), Hereditary Non-Polyposis Colorectal Cancer (HNPCC), active Crohn's disease or active ulcerative Colitis
- (P) Patients have known dipyrimidine dehydrogenase deficiency (DPD)
- (Q) Patients with congenital iron metabolic or hematopoietic diseases
- (R) Patients with synchronous colon cancer
- (S) The Patients with hematologic abnormalities (INR > 1.5, white blood cell (WBC) count < 3,000/ μ L, absolute neutrophil count (ANC) < 1,500/ μ L, platelet count <**

100,000/ μ L, hemoglobin < 9.0 g/dL not caused by tumor treatment) or known hematologic diseases (aplastic anemia, myelodysplastic syndrome (MDS), leukemia, malignant lymphoma, multiple myeloma, hereditary hematologic diseases such as thalassemia, sickle cell anemia, etc.).

(T) The patient has diabetes mellitus

(U) The patient is taking the immunosuppressants Cyclosporine, Tacrolimus, Sirolimus, and Everolimus and Everolimus and anticoagulants (warfarin、NOACs、aspirin)

(V) Patients with The medical, psychological, or social condition that, in the opinion of the investigator, may increase the patient's risk or limit the patient's adherence with study requirements

5.3 Withdrawal criteria

Subject should be withdrawn from the study due to any of the following conditions:

1. The subject voluntarily decides to withdraw her/his consent
2. The subject dies or is lost to follow-up
3. The subject is pregnancy
4. The subject develops disease progression (metastasis or enlargement confirmed)
5. Any clinical adverse event, laboratory abnormality, intercurrent illness, or any occurrence or change in the subject's physically and/or psychologically status giving indication to the investigator that further participation in the study may not be the best interest of the subject
6. The subject does not receive, or is unable to receive, the study intervention, does not keep appointments, or otherwise does not adhere to protocol requirements
7. The subject was enrolled by error and/or it is discovered that the subject does not meet the eligibility criteria after enrollment
8. The study is terminated prematurely by the investigator, research institution, sponsor, IRB or regulatory authorities

For a subject who is withdrawn due to progress confirmed, CT (or MRI) and colonoscopy could be waived at the Early Termination Visit per the investigator's judgments. If a subject is discontinued due to an AE, every effort will be made to follow the event until event resolves or stabilizes at a level acceptable to the investigator.

6. Treatments

6.1.Treatment Administration

A daily dose or high bioavailability curcumin (BCM-95 curcumin) 3g per day is given orally along with the neoadjuvant short-course radiation therapy and chemotherapy.

